hour before bed for 2 weeks to 25 subjects. Subjects will be required to keep a daily log indicating the number of night-time incontinent voids. Subjects will also be asked to complete a validated questionnaire prior to treatment, during the two week treatment phase and two weeks after treatment. The primary outcomes of this study are improvement in the average number of night-time incontinent voids measured by daily log and subjective symptom improvement based on questionnaire comparison at the three phases of the study. Subjects who feel they are having a positive response to TENS treatment and would like to continue participation in the study for an additional 6 weeks may do so.

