If Yes, click Save and then [Click Here For Study Team's CITI Training Records](#) . Please ensure all personnel's training is up to date

[\[reviewer notes-\]](#)

- 1.1 Objective: What is the overall purpose of this research study?** (Limit response to 1-2 sentences.)  
To determine the effects of electrical stimulation of the nerves in the foot on the incidence of nocturnal enuresis (bedwetting) in children.
- 1.2 Specific Aims: List the goals of the proposed study (e.g., describe the relevant hypotheses or the specific problems or issues that will be addressed by the study).**  
Aim #1: To determine if foot stimulation can decrease nocturnal enuresis in children as measured by daily night-time voiding log.  
  
Aim #2: To determine if foot stimulation can improve quality of life questionnaire scores during a 6-week period, with foot stimulation applied during the third and fourth week, as measured by a validated quality of life survey.  
  
Aim # 3: Subjects who feel they are having a positive response to TENS treatment and would like to continue participation in the study for an additional 6 weeks may do so. By collecting this data for an extended period of time we hope to prove long-term efficacy and sustainability in symptom relief, and to ensure no unanticipated adverse outcomes with continued usage
- 1.3 Background: Briefly describe previous findings or observations that provide the background leading to this proposal.**  
Previous animal model studies at the University of Pittsburgh have shown a significant impact on inhibiting bladder overactivity and increasing bladder capacity with neuromodulation techniques, specifically tibial nerve stimulation ([name] et al, 2011). This has been translated into adult clinical trials through the department of urology. Through the use of a commercially available subcutaneous nerve stimulator placed on the dorsum of the foot, we were able to demonstrate a significant increase in bladder capacity and the delay of voiding sensation for up to 5 hours after stimulation in eight healthy subjects (Chen et al, 2014). This prompted the clinical trial approved under IRB PRO13020474 which is currently enrolling patients.  
  

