**Night-time voiding log:**

The subject/parents will be instructed to record a night-time voiding log specifying the number of incontinent episodes per night. This log is included in the IRB application. Subjects/parents will fill out the log for a two week period prior to foot stimulation to determine a baseline average of nocturnal enuresis episodes, during the two week foot stimulation period to measure any acute effect on nocturnal enuresis episodes and finally during the two weeks after stimulation to evaluate any post-stimulation residual benefit.

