**Neuromodulation:**

In the office to calibrate TENS device - skin surface electrodes will be attached to the bottom of one foot for electrical stimulation. The stimulator and electrodes are FDA-approved devices for TRANSCUTANEOUS ELECTRICAL NERVE STIMULATION (TENS) and are commercially available. The stimulation characteristics include a continuous frequency of 5 Hz, pulsewidth 0.2 ms, and intensity 2-4 times the threshold voltage required for inducing

toe twitching - or the intensity that the subject feels comfortable with. The subjects will also be instructed how to use the stimulator and where to attach the electrodes on the foot at the beginning of the study. The investigator will provide the stimulator and electrodes. The subjects will be asked to wear socks to prevent the electrodes from detachment and to stop the stimulation during walking or in any non-resting situation. Subjects will be provided a TENS device and disposable foot pads for two weeks of treatment. Subjects will be asked to use the stimulator for a MINIMUM of 60 minutes in the evening prior to bedtime at home for two weeks. They will be encouraged to use the stimulator for more time than the minimum as long as they accurately record the total duration. Stimulation will be performed during the second and third weeks of the study only.

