#### Questionnaire:

Subjects will complete the quality of life questionnaire attached to this application at the start of the study (prior to week 1) to establish a baseline, after the second week of treatment period (week 4 of study) to determine a treatment effect, and after the sixth week to determine any residual post-treatment effect.

The subjects can call or email the investigators anytime during the 6-week at-home test for questions or any problems encountered. At the end of the 6-week study, the subjects are asked to return the stimulator and night-time voiding log to the investigator's office.

Subjects who feel they are having a positive response to TENS treatment and would like to continue participation in the study for an additional 6 weeks may do so. We will ask that they continue to keep their logs and answer the questionnaires

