**2.17 What are the main outcome variables that will be evaluated in this study?**

1) Number of night-time incontinent episodes per two week period comparing baseline number of voids (first two weeks of study), number during two-week stimulation period (weeks 3-4), and number during two-week after-stimulation period (weeks 5-6).

2) Subjective quality of life measures as recorded by validated quality of life questionnaire prior to study start, after week 4 and after week 6 to evaluate for any differences.

3) For the subjects who continue participation for an additional 6 weeks, we hope to prove long-term efficacy and sustainability in symptom relief, and to ensure no unanticipated adverse outcomes with continued usage

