**3.13 Inclusion Criteria: List the specific criteria for inclusion of potential subjects.**

1. Children ages 5 to 16 years old without any specific neurological disorder or urinary tract infection, clinically diagnosed as having nocturnal enuresis AT LEAST 4 episodes per month by history

2. Currently having no daytime overactive bladder symptoms, i.e. urinary frequency,

urgency, or daytime incontinence

3. Having been assessed for and treated if applicable for behavioral etiologies of nocturnal enuresis - consuming excess fluids or specific bladder irritants

4. Having been assessed for and treated if applicable for constipation

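### Section 2.6 places stimulation in study weeks 2-3 only, while the aims, log, questionnaire schedule and outcome windows all require weeks 3-4

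*Combined protocol and SAP*

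**What the plan says.** The Neuromodulation text in section 2.6 closes with: "Stimulation will be performed during the second and third weeks of the study only".

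The other places that fix the timing read differently:

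- **1.2, Aim #2** describes a six-week period "with foot stimulation applied during the third and fourth week".
- **2.17, outcome 1** compares "baseline number of voids (first two weeks of study), number during two-week stimulation period (weeks 3-4"), and then an after-stimulation count in weeks 5-6.
- **2.6, Night-time voiding log** has families complete the log "for a two week period prior to foot stimulation to determine a baseline average", followed by two weeks on stimulation and two weeks after it. It names no week numbers.
- **2.6, Questionnaire** schedules the second questionnaire "after the second week of treatment period (week 4 of study") and the third "after the sixth week to determine any residual post-treatment effect".
- **CS2.1, abstract** places the questionnaires "prior to treatment, during the two week treatment phase and two weeks after treatment". Read with the week-6 questionnaire, this also ends treatment at week 4.

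**The concern.** The protocol gives two treatment schedules that cannot both be followed. The sentence in 2.6 is the only one in the procedures section that says outright which study weeks carry stimulation, and its closing word rules out week 4.

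The week boundaries matter because they are the comparison. Section 2.3 describes an open-label study that compares each child with himself or herself, and 2.3.1 confirms there is no placebo arm. A misplaced week therefore goes straight into the treatment contrast, with no concurrent group to absorb it. It would also feed the efficacy look after the first 10 subjects (5.13) and the rule in 3.12 to stop recruiting once significance is reached.

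Little in the visible text would catch a family that started a week early. Families who consent at the clinic visit receive the device and the teaching then (4.11.2), and they return it at the end of the six weeks (2.6). Section 2.7 answers No to research follow-up procedures. The only scheduled monitoring call, in 5.13, belongs to the extension. The training text in 2.6 names no weeks.

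**Working it through.** **Step 1. Rebuild the schedule from the stated durations.** The log text in 2.6 gives 2 weeks before, 2 weeks during and 2 weeks after stimulation. 2 + 2 + 2 = 6 weeks, which matches the six-week study in 2.6 and 5.7. Counting from week 1, stimulation falls in weeks 3-4. Weeks 2-3 is not reproduced.

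Two readings might rescue the sentence, and neither does:
- *Numbering from week 0.* The questionnaire text counts from week 1, and the outcome windows end at week 6.
- *A one-week baseline.* The log text and 2.17 both require two weeks.

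**Step 2. Put each schedule into the calendar windows of 2.17.**

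| Window (2.17) | Stimulated weeks if stimulation is in weeks 3-4 | Stimulated weeks if stimulation is in weeks 2-3 |
|---|---|---|
| Baseline, weeks 1-2 | 0 of 2 | 1 of 2 (week 2) |
| Stimulation, weeks 3-4 | 2 of 2 | 1 of 2 (week 3) |
| After, weeks 5-6 | 0 of 2 | 0 of 2, starting one week late |

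With stimulation ending at week 3, the week-4 questionnaire comes one week after stimulation instead of at its end. The last questionnaire comes 6 - 3 = 3 weeks after instead of 2. The pre-study questionnaire is unaffected.

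**Step 3. Share of the baseline-versus-stimulation contrast that is kept.** Let B be the weekly episode rate without stimulation and E the full weekly reduction. Let *a* be the share of E reached in the first stimulated week and *c* the share that persists in the first week off. The documents give neither *a* nor *c*, so both are shown as ranges.

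- Stimulation in weeks 3-4: contrast = 2B - (2B - aE - E) = E(1 + a).
- Stimulation in weeks 2-3: baseline = 2B - aE; stimulation window = 2B - E - cE; contrast = E(1 + c - a).
- Share kept = (1 + c - a)/(1 + a).

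| a | c = 0 | c = 0.5 | c = 1 |
|---|---|---|---|
| 1 | 0% | 25% | 50% |
| 0.75 | 14% | 43% | 71% |
| 0.5 | 33% | 67% | 100% |
| 0.25 | 60% | 100% | 140% |

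The contrast is diluted when c < 2a and inflated when c > 2a.

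**Step 4. The same thing in episodes, for illustration only.** Section 3.13 admits children with "AT LEAST 4 episodes per month by history". At that threshold, and taking 30.44 days per month, 4/30.44 × 14 = 1.84 episodes per two weeks. Assume that stimulation halves the rate (E = B/2) and that there is no carry-over (c = 0).

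| Case | Baseline | Stimulation | After | Contrast |
|---|---|---|---|---|
| a = 1, stimulation weeks 3-4 | 1.84 | 0.92 | 1.84 | 0.92 |
| a = 1, stimulation weeks 2-3 | 1.38 | 1.38 | 1.84 | 0 |
| a = 0.5, stimulation weeks 3-4 | 1.84 | 1.15 | 1.84 | 0.69 |
| a = 0.5, stimulation weeks 2-3 | 1.61 | 1.38 | 1.84 | 0.23 |

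The shares kept, 0/0.92 = 0% and 0.23/0.69 = 33%, agree with step 3.

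**Step 5. Windows set by phase instead.** If stimulation runs in weeks 2-3 and nights are assigned to before, during and after by when the device was actually used, no window is mixed. The baseline is then week 1 alone: 7 nights against the 14 that the log text requires.

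**The case against.** The strongest reply is that nobody will act on this sentence. The intended schedule is not in real doubt, since the document's own durations lead back to weeks 3-4. Within 2.6 itself the log and questionnaire text outweigh it two to one. Families act on the training, the log form and the consent material, not on an application form, and those are either silent on weeks or not visible here. Damage to the voiding-log contrast needs two things together: families being told weeks 2-3, and counts still being cut by calendar week. The log text describes phases, and 2.17 labels its windows by phase as well as by week, so an analyst might well assign nights by phase. Finally, the size depends on two unknown quantities and runs from total loss to inflation, and the episode illustration assumes an effect that the documents do not state.

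Most of this stands as a limit on the claim. The sentence is very probably a slip, the harm is conditional, the log and abstract support weeks 3-4 by inference and not in so many words, and the episode figures add scale but no evidence. None of it removes the contradiction. Staff cannot comply with both 2.6 and 2.17, and what families are told cannot be confirmed from these documents. Assigning nights by phase would still break the two-week baseline requirement.

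**Conclusion.** The concern holds. The sentence is wrong as written and conflicts with every other timing statement in the protocol; that part rests on no assumption.

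The consequence rests on two conditions: that families follow the sentence, and that the 2.17 windows are applied by calendar week. If both hold, the main before-versus-during contrast can lose anything up to all of its size when onset is fast and carry-over is short. It can be overstated when onset is slow and carry-over is long. Without information on onset and persistence, neither the amount nor the direction can be fixed. An unnoticed error would be hard to repair once the data are in, unless the dates of stimulation can be recovered from the log, which is not reproduced here. That, set against a very cheap correction, is the reason to require it.

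**What to change.** In the Neuromodulation text of section 2.6, replace the reference to the second and third weeks with the third and fourth weeks of the study only. Check that the uploaded log and whatever instructions families receive give the same weeks. The schedule then reads weeks 1-2 baseline, 3-4 stimulation and 5-6 after, in agreement with Aim #2, the log, the questionnaires and 2.17.

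As an option, have families record the dates of stimulation next to the duration they are already asked to record, so that the assignment of nights to windows can be verified.

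The cost is one phrase and a check of the log and family instructions.

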#### TENS Unit Training:

The training session will take place in a patient room in the office of pediatric urology. The training will be conducted in person by [name] with the parent(s) and child in the room. [name] will explain the device, how it works and how to use it to the parent(s) along with a detailed user manual that is provided with the stimulator. The parent(s) will be instructed how to place the stimulation pads on the child's foot (most distal covering the planar bridge of the foot and more proximal pad over the medial edge of the foot). The parent(s) will then be instructed on how to connect the two electrode wires to the device and turn it on. The device settings are preprogrammed at time of sale, so no frequency change adjustments need to be made. The parent(s) will incrementally increase the voltage on the device until the child elicits a response of involuntary contraction of at least two toes of the foot including the great toe. Stimulation will be continuous for 5 minutes assessing the child's comfort level. If the child is obviously uncomfortable at the level of voltage required for involuntary motor movement and does not perceive they would be able to stimulate in this fashion at home for periods of up to one hour, they will not be eligible for the study.

#### Questionnaire:

Subjects will complete the quality of life questionnaire attached to this application at the start of the study (prior to week 1) to establish a baseline, after the second week of treatment period (week 4 of study) to determine a treatment effect, and after the sixth week to determine any residual post-treatment effect.

The subjects can call or email the investigators anytime during the 6-week at-home test for questions or any problems encountered. At the end of the 6-week study, the subjects are asked to return the stimulator and night-time voiding log to the investigator's office.

Subjects who feel they are having a positive response to TENS treatment and would like to continue participation in the study for an additional 6 weeks may do so. We will ask that they continue to keep their logs and answer the questionnaires

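### No quality-of-life questionnaire is taken just before home stimulation, so the week-4 treatment effect includes any change during the untreated run-in

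*Combined protocol and SAP*

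**What the plan says.** The abstract (CS2.1) lists as a primary outcome "subjective symptom improvement based on questionnaire comparison at the three phases of the study". Section 2.6 (Questionnaire) sets the first form "at the start of the study (prior to week 1) to establish a baseline", the second "after the second week of treatment period (week 4 of study) to determine a treatment effect", and a third after week 6. Section 2.17 gives the same three time points: "Subjective quality of life measures as recorded by validated quality of life questionnaire prior to study start, after week 4 and after week 6".

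The voiding log is aligned differently. Section 2.6 (Night-time voiding log) states: "Subjects/parents will fill out the log for a two week period prior to foot stimulation to determine a baseline average". Its baseline therefore runs directly up to stimulation.

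The documents disagree on which weeks are stimulated. Aim #2 in section 1.2 describes quality of life "during a 6-week period, with foot stimulation applied during the third and fourth week", and section 2.17 also gives weeks 3-4. Section 2.6 (Neuromodulation) says instead: "Stimulation will be performed during the second and third weeks of the study only".

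Two other places are looser on questionnaire timing. The abstract puts the forms "prior to treatment, during the two week treatment phase and two weeks after treatment", so the second falls during treatment and not after it. Section 5.7 uses the word weekly in a phrase that covers both the log and the questionnaires.

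The study is open-label with no placebo arm and compares each subject before and after treatment (2.3, 2.3.1). Section 2.18 names the t-test and ANOVA, and no method for separating run-in change.

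**The concern.** The week-4 form is the one the protocol uses to show a treatment effect, but its comparator is taken before the run-in. Anything that moves quality of life between enrolment and the first home session is counted with the effect of stimulation.

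Some movement is plausible. Children are recruited at a clinic visit for enuresis (4.2). Assessment and, where applicable, treatment of fluid habits, irritants and constipation is part of eligibility (3.13). Consent, equipment and teaching may all be given at one visit (4.11.2), and the training includes a five-minute trial stimulation (2.6). None of this shows that a shift occurs or which way it goes. It could create an apparent effect or hide a real one.

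The nightly log can reveal run-in change in enuresis, but not in quality of life. Section 3.12 also stops recruitment once significance is reached, without naming the outcome, so a shift in this score could contribute to that decision.

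**Working it through.** **Plan's own figure.** There is none to reproduce. The documents give no alpha, SD, effect size or named contrast (2.18), and the 25 subjects are not derived from a calculation (3.12).

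**Step 1: count the weeks between the first form (week 0) and the second (end of week 4).**

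| Stimulated weeks | Source | Untreated before | Treated | Untreated after |
|---|---|---|---|---|
| 3-4 | 1.2 Aim #2; 2.17; consistent with the log text in 2.6 | 2 | 2 | 0 |
| 2-3 | 2.6 Neuromodulation | 1 | 2 | 1 |

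Under weeks 3-4, 2/4 = 50% of the interval is untreated run-in. Under weeks 2-3, the two anchors in 2.6 for the second form also separate: the second treatment week ends with week 3, not week 4. Under neither schedule does a form fall just before home stimulation.

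**Step 2: what a shift could do (illustration).** Assumptions not in the documents: paired t-test, two-sided 0.05, n = 25, a run-in shift that persists, and no other change during stimulation. With the shift d in SDs of the change score, the noncentrality is d × √25 = 5d, on 24 degrees of freedom.

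| Run-in shift d | 5d | Significant with no device effect | Power for a 0.5 SD effect if the shift opposes it |
|---|---|---|---|
| 0 | 0 | 5.0% | 67.0% |
| 0.1 | 0.5 | 7.7% | 48.4% (net 0.4) |
| 0.2 | 1.0 | 16.1% | 30.2% (net 0.3) |
| 0.3 | 1.5 | 30.2% | 16.1% (net 0.2) |

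**Step 3: what the week-6 form can do.** Let D be the total run-in shift, persisting to week 6, and let each score average status over the recall window. With recall of two weeks or less, the week-4 and week-6 scores both contain D, so week 4 minus week 6 contains D − D = 0. A benefit B that lasts to week 6 also gives B − B = 0. The contrast is therefore largely free of a persisting run-in shift, but it cannot show a lasting benefit.

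**Step 4: what an added form at week 2 can do (weeks 3-4 schedule).** Suppose the shift builds evenly over weeks 0-2 and then holds.

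- No look-back: added form = D, week 4 = D, remainder 0.
- One week: added form = 0.75D, remainder 0.25D.
- Two weeks: added form = 0.5D, remainder 0.5D. The log has the same dilution: mean of weeks 3-4 (D) minus mean of weeks 1-2 (0.5D).
- Four weeks: week 4 = 0.75D, added form = 0.25D, remainder 0.5D, against 0.75D without the added form.

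If the shift occurs at once after enrolment, the remainder is 0 for recall up to two weeks and 0.5D at four weeks. With a two-week recall and a gradual 0.3 SD shift, 0.15 SD remains, and the rejection rate falls from 30.2% to 11.1% (taking the SD of the change score as unchanged).

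**The case against.** A reader might infer that nothing in the design can separate run-in change from change during stimulation. The documents do not support that. The week-6 form is an off-stimulation measurement, and a fall in quality of life between week 4 and week 6 would not be explained by a run-in shift that persists. This stands, but only in part: a lasting benefit, which section 2.6 also looks for, would cancel in the same contrast.

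Section 5.7 could be read as requiring weekly questionnaires, which would supply a pre-stimulation score. That is the weaker reading. The word may apply to the log alone, and sections 2.6 and 2.17 both list exactly three forms.

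An enrolment baseline also fits Aim #2, which speaks of the whole six-week period. The criticism therefore bites on calling the week-4 change a treatment effect. Softening that label would be cheaper, but the abstract's primary comparison would still be unable to isolate the stimulated weeks.

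Finally, the absence of a control group is the larger limitation, and the benefit of an added form depends on an instrument that is an upload (2.8) and not shown. Both points stand and limit the weight of this one. They do not remove it, because the run-in already exists and one form would make use of it.

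**Conclusion.** The point holds and is worth considering as a modest improvement to an uncontrolled pilot. It follows from the protocol's own schedule: two of four weeks in the baseline-to-week-4 contrast are untreated under weeks 3-4, and one before plus one after under weeks 2-3.

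The 30% figure is an illustration. It rests on an assumed 0.3 SD persisting shift, n = 25, a two-sided 0.05 paired t-test, no device effect and no other change. A reader might infer that the quality-of-life result is biased in the device's favour. The documents do not support that, since they give neither size nor direction for any run-in change. The contradiction over the stimulated weeks is a separate defect that needs correcting in any case; it changes the length of the untreated gap, not its existence.

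**What to change.** 1. Reconcile section 2.6 (Neuromodulation) with Aim #2, the log and questionnaire text of 2.6, and 2.17 on which weeks are stimulated. Reconcile the abstract and 5.7 with 2.6 and 2.17 on when questionnaires are completed.
2. Keep the form before week 1. Add one dated home questionnaire at the end of the log baseline, before the first home stimulation, handed out with the log. Amend 2.6, 2.17 and the abstract to match.
3. State the instrument's recall period. If it is about two weeks or less, use the added score as the baseline for the week-4 and week-6 contrasts. If it is longer, report both sets of contrasts and say that run-in change is only partly removed.
4. Report the enrolment-to-pre-stimulation change separately.
5. Analyse all forms in a repeated-measures model with time point as a factor, of a kind that retains subjects with incomplete forms. Do not substitute enrolment scores for a missing added form: that would mix two baselines and bring the run-in shift back for those subjects. Treat an added form dated after the first home stimulation as missing for that time point.
6. Reconcile the added form with the non-compliance wording in 5.7, so that its status there is clear.

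The cost is one extra form per family (25 forms at n = 25), some missing or late forms because 2.6 schedules no contact at that point, and an amendment. The choice of model matters: if 5 of 25 forms were missing (an assumption) and those subjects were dropped, power for a 0.5 SD effect would fall from 67% to about 56% at n = 20, under the same test assumptions. Placebo response and time trends during the stimulated weeks would remain after this change.
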